17.8.7 Safety Analysis

Adverse events (AE) will be presented by seriousness, severity and relation to treatment by treatment group. The number of reports, the number of subjects, and the incidence (percent of subjects) will be tabulated by study arm.

17.8.8 Handling of Missing Data

Missing value will not be imputed and will be left "as-is". For the time to first SBM analysis, subjects with no known SBM will be considered left censored.

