In addition, patients will undergo a physical examination including digital rectal examination, vital sign measurements and blood tests.

Patients will then fill in the Rome III questionnaire to confirm the diagnosis of Chronic Idiopathic Constipation and fill out the Bristol Stool Scale. Findings will be recorded on the eCRF.

Eligible patients will then be asked to refrain from taking any medication or supplement they are using to relieve their constipation, and will perform a self-assessment of their normal spontaneous bowel movements for 14 days (run-in period), on the eDiary. Patients will also be asked to record clinical symptoms and usage of any medication or supplement on the eDiary during the run-in period.

After 14 days the patients will visit the medical center for the baseline visit. Eligibility will be re-assessed and confirmed based on the patient's completed eDiary and Rome III questionnaire. The patient will be trained in the medical center to use the base unit. He will activate himself the first capsule and will ingest it in front of the medical staff. All the other capsules will be ingested from the home of the patient. Only the first ingestion will take place in the medical center.

During the treatment period, patients will ingest Vibrant Capsule using the following sequence: one per day for 2 days, 1 day without, one per day for 2 days, 1 day without, etc. The patient will ingest a total of 28 capsules in 6 weeks considering the sequence.

Capsule intake will always be performed at the same time: during the evening, between 9 PM and 10 PM.

Doc No: 220CLD

Rev: 03 Date: August 26, 2016

Page 43 of 93

After 6 weeks, treatment will be ceased and patients will visit the medical center one last time for evaluation and completion of Rome III questionnaire, Bristol Stool Scale and other assessments.

Patients will be instructed to complete a simple patient eDiary throughout the duration of the study. This will include daily recordings of number and time of bowel movements, clinical symptoms and medication/supplements usage, including rescue medication.

Please refer to section 15.15 for a detailed study schedule.

Data collection will include physician identification, investigational device identification data and usage of the capsule. This data will be documented on the eCRF, together with the occurrence of any adverse events during the capsule usage.

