15.9 Treatment

On day 0 (baseline visit), the patient will arrive to the clinic. Eligibility will be reassessed and confirmed based on the Rome III questionnaire and on the patient's completed diary. Based on the Vibrant Capsule's intended use, patients need to have an average of at least 1 SBM per week but less than 3 SBM per week during the two weeks of run-in.

The Bristol Stool Scale will be completed.

Eligible patients will take the Vibrant Capsules. The study is open-label.

Treatment duration is 6 weeks.

The patient will be trained by the study coordinator to activate the Vibrant Capsules using the base unit. After an oral explanation, the patient will read the label, and the study coordinator will make sure the patient fully understands how to use the base unit. The patient will then activate his/her first capsule, in front of the study coordinator, and swallow it.

The patient will be released home with the base unit and capsules for the first three weeks of treatment. He/She will be asked to continue with the daily completion of the eDiary. Actual point of enrollment for the patient is considered the day of first capsule intake.

Patients will be asked to refrain from any medication or supplement they are using to relieve their constipation, throughout the treatment period. A rescue treatment will be authorized upon need (refer to section 15.10 for details).

Capsule intake will be performed during the evening between 9 PM and 10 PM. Only the first intake, which is in the medical center, will not take place at such a time.

Doc No: 220CLD

Rev: 03 Date: August 26, 2016

Page 46 of 93

Half of the capsules the patient is scheduled to take will be provided at the baseline visit. The patient will be provided with the second half of the capsules during a mid-treatment visit to the medical center (day 21).

The first week of treatment, the patient will receive two short phone calls from the study coordinator. Starting the second week of treatment, he will receive one phone call per week.

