17.2.2 Secondary Efficacy Endpoints

Secondary efficacy endpoints include:

- Ease of use
- CSBM success rate, defined as as an increase from the run-in period of at least one weekly Complete Spontaneous Bowel Movement (CSBM) during at least 3 of the 6 weeks of treatment. Subjects with less than 2 weeks (with at least 5 days per week) of valid diary during the treatment period will be considered as non-evaluable.
- Change from baseline in weekly number of Spontaneous Bowel Movement (SBM).
- Change from baseline in weekly number of Complete Spontaneous Bowel Movement (CSBM).
- Change from baseline in average stool consistency, using the Bristol Stool Scale
- Change from baseline in average bloating.
- Change from baseline in average abdominal gas.
- Change from baseline in average abdominal pain.
- Change from baseline in average straining.
- Change from baseline in abdominal discomfort.
- Change from baseline in average abdominal pain during defecation.
- Time to occurrence of spontaneous bowel movement after capsule.

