17.4 Sample size

The chosen sample size is 120 subjects who will be enrolled and complete the 6 treatment weeks.

The final sample size will be determined following the completion of the interim analysis, based on the efficacy of the new frequency of vibration capsule.

The sample size account for a potential 10% of drop-outs.

The sample size will be increased to at least 134 to account for a potential 10% of dropouts, as needed.

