17.8.5 Efficacy Analysis

The subject's success status (i.e. if the subjects achieve an increase from baseline of at least 1 weekly SBM during at least 3 out of the 6 treatment weeks) will be calculated. The success rate will be presented along with its exact binomial two sided 95% Confidence Intervals (CI).

Ease of Use will be presented in a tabular form.

Doc No: 220CLD

Rev: 03 Date: August 26, 2016

Page 58 of 93

The CSBM success rate will be analyzed in the same manner.

The change from baseline in number of weekly SBM will be modeled with an Analysis of Covariance (ANCOVA) model, with baseline weekly number of SBM and site as covariates. The adjusted means of the change from baseline will be presented along with its 95% CI.

The change from baseline in count of weekly CSBM, and in symptoms, will be analyzed with similar ANCOVA models, with their respective baseline values as covariate.

Time to occurrence of SBM after intake of the first Vibrant capsule will be assessed and presented by Kaplan-Meier curves.

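### Subjects with no SBM are labelled left censored in the time-to-first-SBM analysis; they are right censored, and the rule does not fit the Kaplan-Meier method the plan names

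*Combined protocol and SAP*

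**What the plan says.** Section 17.2.2 lists among the secondary efficacy endpoints "Time to occurrence of spontaneous bowel movement after capsule". Section 17.8.5 gives the method and the time origin: "Time to occurrence of SBM after intake of the first Vibrant capsule will be assessed and presented by Kaplan-Meier curves". Section 17.8.8, after ruling out imputation, adds the only handling rule for this endpoint: "For the time to first SBM analysis, subjects with no known SBM will be considered left censored".

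Three other statements fix what is observed. Section 15.9 has the first capsule swallowed in front of the study coordinator, and "Actual point of enrollment for the patient is considered the day of first capsule intake". The same section says "Treatment duration is 6 weeks". Section 15.1 describes the eDiary: "This will include daily recordings of number and time of bowel movements". The plan states no censoring time and names no method for left-censored data.

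**The concern.** The rule describes these subjects the wrong way round. A left-censored time is one where the event is known to have happened before some point, at an unknown moment. A subject observed from a known first capsule with no SBM recorded is the opposite case: as far as the diary shows, the event has not yet happened.

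Sections 17.8.5 and 17.8.8 therefore cannot both be followed as written. The analyst must either depart from the text or replace the named method with one that accepts left censoring. The second course would count every subject without an SBM as having had one, which makes the device look faster and more uniformly effective. With a single arm, there is no comparator curve to expose the error.

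**Working it through.** The documents give no figure for this analysis, so there is none to reproduce. The check is first one of definition, then of size.

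**Definition.** Let T be the time from first capsule to first SBM, and c the last valid diary day (at most about day 42).

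- Right censored: T > c. Left censored: T < c.
- The origin is known (section 15.9), and events are recorded daily from then on (section 15.1). No recorded SBM by c means T > c.
- Kaplan-Meier multiplies (1 − d/n) over event days, where n counts subjects still under observation without an event. Right-censored subjects stay in n until c. A subject with T < c has no defined place in n.
- With only exact and left-censored times, the nonparametric maximum likelihood (Turnbull) estimate puts all probability at or before the last time. The share without an SBM at day 42 is then 0, whatever the true share.

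**How many subjects could be affected.** The documents do not give f, the share with no recorded SBM. The available anchors are the entry rule in section 15.9 ("patients need to have an average of at least 1 SBM per week but less than 3 SBM per week"), the 42-day treatment period, and the 10% dropout and 134 subjects in section 17.4. Assume Poisson SBMs at r per week, no treatment effect, and dropout uniform over the first D days:

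f = 0.9·exp(−6r) + 0.1·(1 − exp(−rD/7))/(rD/7)

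| r per week | D (days) | Completer term | Dropout term | f | Of 134 |
|---|---|---|---|---|---|
| 1 | 42 | 0.00223 | 0.01663 | 1.9% | 2.5 |
| 1 | 14 | 0.00223 | 0.04323 | 4.5% | 6.1 |
| 2 | 42 | 0.00001 | 0.00833 | 0.8% | 1.1 |
| 2 | 14 | 0.00001 | 0.02454 | 2.5% | 3.3 |

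In these cases nearly all of f is early withdrawal.

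**Effect on the curve.** Simulation under the same assumptions used n = 134, 600 replicates and times rounded up to the diary day. It compared right-censored Kaplan-Meier with the Turnbull estimate when the same subjects are left censored. Share without an SBM at day 7:

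| r per week | D (days) | Right censored | Left censored | Gap (points) |
|---|---|---|---|---|
| 1 | 42 | 37.0% | 35.7% | 1.3 |
| 1 | 14 | 36.7% | 33.6% | 3.1 |
| 2 | 42 | 13.7% | 13.3% | 0.4 |
| 2 | 14 | 13.7% | 12.7% | 1.0 |

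The right-censored values agree with the true exp(−r) of 36.8% and 13.5% to within simulation error. The left-censored estimate at day 42 is 0 in every case.

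**Followed subjects who never have an SBM.** This is an assumption-only illustration. Take true S(t) = f + (1 − f)·exp(−λt), with λ set so that the true median is 2.0 days. Left censoring returns exp(−λt). For f = 2%, exp(−2λ) = 0.48/0.98, so λ = 0.357. The left-censored median is 0.693/0.357 = 1.94 days, and the day-7 share is 8.2% against a true 10.1%. The same steps give 1.97 days and 8.5% against 9.4% for f = 1%, and 1.86 days and 7.3% against 11.9% for f = 5%.

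**The case against.** The strongest reply is that this is a slip of one word. Section 17.8.5 names Kaplan-Meier, which steers any competent programmer to right censoring, and then nothing is biased. Harm requires abandoning the named method for one the plan never mentions. The endpoint is one of about a dozen secondaries in a single-arm study described as mainly descriptive, and no decision rule uses it. All of that stands and limits the weight of the point. It does not make the rule correct: this is the plan's only instruction for a listed efficacy endpoint, and the analyst has to contradict it to do the analysis properly.

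The illustration for followed subjects who never have an SBM is also open to challenge. Under the Poisson model a subject followed for six weeks has no SBM with probability exp(−6) = 0.25% at 1 per week, so values of 1% to 5% are 4 to 20 times higher. The 2.0-day median is not in the documents either. That is fair. Differences between subjects could raise f, but nothing in the documents supports a particular value, so the dropout cases are the better guide to size.

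Diary gaps are the third objection. The rule speaks of no known SBM, and section 15.9 anticipates unfilled diary days. A first SBM inside a gap may have gone unrecorded, so right censoring at the last diary day treats the gap as event-free. This is a fair refinement. An SBM known to lie within a gap would be interval censored, but a subject with no recorded SBM still does not become left censored.

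**Conclusion.** The concern holds. The censoring direction in section 17.8.8 is wrong by definition, it does not fit the method in section 17.8.5, and no other section corrects it or states when these subjects are censored.

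The numerical effect is zero if ordinary right censoring is used, which is the likely outcome. Under literal use with a left-censoring estimator, the error favours the device: day-42 survival is forced to 0, and the day-7 share without an SBM falls by 0.4 to 3.1 points in the dropout cases. The top figure needs the lowest entry rate and every dropout leaving within 14 days. These sizes rest on the Poisson, no-effect and 10% dropout assumptions. Dropping subjects with no valid post-baseline assessment (section 17.7.1) and using the per-protocol set for efficacy (section 17.7.3) could lower f further.

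The primary SBM success rate and its exact confidence interval are untouched. The sentence should be corrected, but the stakes are limited.

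**What to change.** Replace the sentence in section 17.8.8 with: *Subjects with no SBM recorded after the first capsule will be right censored at their last valid diary day in the treatment period (or at withdrawal, if earlier).* Keep the Kaplan-Meier presentation in section 17.8.5. This corrects the direction and supplies the missing censoring time. As a refinement, add a line defining a valid diary day and saying how unfilled days before the censoring day are treated.

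The cost is a sentence or two of text, with no new data and no change to study conduct. Because the text sits in the combined protocol, the change may have to follow the amendment route in section 26.

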18. DATA MONITORING PLAN

The Principal Investigator and his study staff will monitor all data accrual. In addition a data monitor will visit the study site during the study and review the progress of the clinical trial including safety data and ensure as possible that it is conducted, recorded, and reported in accordance with the protocol, Good Clinical Practice (GCP), and the applicable regulatory requirement(s). A written report form will be issued after each

Doc No: 220CLD

Rev: 03 Date: August 26, 2016

Page 59 of 93

monitoring visit (including initiation and close out visits). The monitoring visit report will include a summary of what the monitor reviewed and the monitor's statements concerning the significant findings/facts, deviations and deficiencies, conclusions, actions taken or to be taken and/or actions recommended to secure compliance. The investigator/institution should provide direct access to source data/documents for trial-related monitoring and auditing, IRB/IEC review and inspection by the appropriate regulatory authority/ies.

Verification during monitoring visit will include:

- 1. That the investigator has adequate qualifications and resources and remains adequate throughout the trial period, that facility, including laboratories, equipment, and staff, are adequate to safely and properly conduct the trial and remain adequate throughout the trial period.
- 2. Verifying for the investigational product(s):
 - a. That storage conditions are acceptable.
 - b. That the investigational product(s) are supplied only to subjects who are eligible to receive it according to protocol and no other use is being done with the Vibrant devices.
 - c. That the receipt, use, and return of the investigational product(s) at site are controlled and documented adequately and that supplies delivery notes are confirmed upon reception throughout the trial.
 - d. That the unused investigational product(s) at sites will be returned.
- 3. Verifying that the investigator follows the approved protocol and all approved amendment(s), if any.
- 4. Verifying that written informed consent was obtained before each subject's participation in the trial.
- 5. Ensuring that the investigator receives the current Investigator's Brochure, all documents, and all trial supplies needed to conduct the trial properly and to comply with the applicable regulatory requirement(s).
- 6. Ensuring that the investigator and the investigator's trial staff are adequately informed about the trial.
- 7. Verifying that the investigator and the investigator's trial staff are performing the specified trial functions, in accordance with the protocol and any other written agreements, and have not delegated these functions to unauthorized individuals.
- 8. Verifying that the investigator is enrolling only eligible subjects and at sufficient recruitment rate.
- 9. Verifying that source documents and other trial records are accurate, complete, kept up-to-date and maintained.
- 10. Verifying that the investigator provides all the required reports, notifications, applications, and submissions, and that these documents are accurate, complete, timely, legible, dated, and identify the trial.
- 11. Checking the accuracy and completeness of the CRF entries, source documents and other trial-related records against each other.

Doc No: 220CLD

Rev: 03 Date: August 26, 2016

Page 60 of 93

12. The data required by the protocol are reported accurately on the CRFs and are consistent with the source documents.

- 13. Adverse events, concomitant medications and intercurrent illnesses are reported in accordance with the protocol on the CRFs.
- 14. Visits that the subjects fail to make, tests that are not conducted, and examinations that are not performed are clearly reported as such on the CRFs.
- 15. All withdrawals and dropouts of enrolled subjects from the trial are reported and explained on the CRFs.
- 16. Verifying that the investigator had answered all of the queries that came up from inspection of the CRFs or other trial material.
- 17. That the investigator is maintaining the essential documents.
- 18. Verifying that deviations from the protocol, SOPs, GCP, and the applicable regulatory requirements are reported by the investigator to the IRB/IEC and that appropriate actions were taken to prevent recurrence of the detected deviations.

Should there be an unexpected number of device failures or related complications that increase the risks to the participants, or critical efficacy endpoints at intervals that are not satisfying, the study will be halted and analysis performed to determine whether to continue, modify the protocol, or close the study.

19. DATA CONFIDENTIALITY

Each patient will be identified by his/ her initials and a unique patient identification number. Source data will be stored with source documents. The Investigator Site Files (ISF) will be held in a secure area. The subject's name and personal data will remain confidential and will not be published in any way. However, the sponsor's monitor or representative and regulatory representatives, auditors and inspectors may have access to medical files in order to verify authenticity of data collected.

20. FUNDING

The study is funded by Vibrant Ltd.

21. ETHICS

Prior to study initiation the site shall obtain EC or IRB approval of the study. A copy of the written EC approval must be provided to the sponsor prior to the start of the study. Any changes in the study protocol, informed consent forms, or investigator must be reapproved by the EC or IRB and the approval documented. All patients enrolled in the study will provide their consent prior to entering the study. An informed consent form shall be signed and dated by the patient. The investigator will retain the forms as part of the study records.

Doc No: 220CLD

Rev: 03 Date: August 26, 2016

Page 61 of 93

This study will be executed in accordance with the Declaration of Helsinki, in agreement with the guidelines for conducting a clinical investigation in accordance with the principles of ICH GCP outlined in the E6 document. By signing the present protocol, the investigator commits to carry it out in accordance with local legal requirements.

Other investigator responsibilities relative to the EC include the following:

- 1. During the conduct of the study, the investigator will submit progress reports to the EC as required, and request re-review and approval of the study at least once a year;
- 2. The investigator will report immediately to the EC of any unexpected serious adverse events that occur during the study, and provide the sponsor with a copy of the correspondence;
- 3. If the sponsor notifies about serious adverse events reported in other studies using this device, the investigator must report that information to the EC;
- 4. As required, the investigator must obtain approval from the EC for protocol amendments and for revisions to the consent form or subject recruitment advertisements:
- 5. The investigator should provide the EC with any other information it requests before or during conduct the study;
- 6. The investigator must maintain a file of study-related information that includes all correspondence with the EC;
- 7. The investigator must notify EC when study is completed (i.e. after the last study visit of the final study subject);
- 8. After study completion (within 12 months is recommended) the investigator should provide the EC with a final report on the study. The recommended components of a final report are as follows; dates of study start and completion, number of subjects enrolled/treated, number of subjects who discontinued participation early and reason why, itemization and discussion of any serious adverse event.

22. INFORMED CONSENT

Written informed consent must be obtained from each study subject. The subject will be asked to read the informed consent form and to sign the form to indicate consent to participate in the study.

The investigator will explain carefully to the subject the research nature of the study. The scope and aims of the research will be described together with known or foreseeable benefits, risks and discomforts that subjects may experience. Appropriate alternative treatments will be discussed so that the subject may determine whether or not he or she wishes to participate in the study. The subject must understand that throughout the study his or her participation remains voluntary and protected by the Declaration of Helsinki. The investigator is responsible for obtaining written (or witnessed) informed consent from potential subjects prior to study entry. Subjects will be given time to read the informed consent and ask any questions before being asked to sign the form. The informed consent (approved by the sponsor and the Ethics Committee) must be signed and dated by the subject and the investigator. One copy of the signed consent will be

Doc No: 220CLD

Rev: 03 Date: August 26, 2016

Page 62 of 93

given to the subject, a second copy will be sent to the referral investigator and the original will be retained by the investigator.

Subjects may withdraw their consent to participate in the study at any time without prejudice. The investigator may withdraw a subject if, in his clinical judgment, it is in the best interest of the subject or if the subject cannot comply with the protocol. Attempts should be made to complete any examinations and the sponsor must be notified of all withdrawals.

Should a protocol amendment be made, the subject's consent form may be revised to reflect the changes of the protocol. It is the responsibility of the investigator to ensure that an amended informed consent is approved or reviewed by the EC, and that it is signed by all subjects subsequently entered in the study and those currently in the study, if affected by the amendment.

